## 8.3 Procedure for Reporting Adverse Events and Device Deficiencies

The procedure for the reporting of adverse event and device deficiency reporting is detailed in flowchart 1.

# 8.3.1 Adverse Event Reporting

In case of an occurrence of an AE assessed as non serious, the Investigator will complete the appropriate eCRF form within 30 days of awareness of the event-

In case of an occurrence of an AE assesses as serious (SAE), the Investigator shall inform the sponsor **within 24 hours of awareness of the event** by completing the SAE form in the eCRF and / or by writing an email to [contact].

The Sponsor will report any SAE to the EC within 7 days of awareness of the event by email to the following address: [contact].

It is recognized that in many cases SAEs will be treated in a medical rather than a dental environment and the Investigator may not have immediate knowledge of the event. The Investigator should report any SAE as soon as he/she has knowledge of the event within the above timeframe irrespective of when the actual event occurred.

If an SAE constitutes a serious incident or a serious public health threat, the additional steps detailed in flowchart 1 will be followed.

[figure not shown]
#### 8.3.2 Device Deficiency Reporting

DDs without SADE potential should be reported by the investigator to the sponsor within 30 days of awareness of the event using the Device Deficiency Form.

[figure not shown]
DDs with SADE potential shall be reported the same way as SAEs (see previous paragraph).

## Flowchart 1: Adverse event and device deficiency reporting

\*\*MDR; \*\*\*Agencia Española de Medicamentos y Productos Sanitarios; \*\*\*\*Straumann procedure QMS-CORP-000297, in line with MDR

# 8.4 Monitoring of Patients with Adverse Events

Any AE that occurs during the course of this study must be monitored and followed-up by the Investigator until one or more of the following have occurred:

- the AE is resolved,
- Pathological laboratory findings have returned to normal,
- steady state has been achieved, or
- it has been shown to be unrelated to the study devices.

The outcome of an event will be pursued until resolution or until the last data queries are issued following the patient's last study visit. For screening failures, ongoing AEs, ADEs and DDs must be followed and updated until the date the patient is deemed a screening failure. For patients documented as lost to follow-up, ongoing AEs, ADEs, and DDs will not be followed.

It is the responsibility of the sponsor to cooperate with the Investigator to assure that any necessary additional therapeutic measures and follow-up procedures are performed.

## 8.5 Pregnancy

If a female patient becomes pregnant during the course of the study, the study visits should be completed as scheduled. Any study assessments that could potentially interfere with the pregnancy should be avoided until after the pregnancy (e.g., radiographs, etc.). The pregnancy should be recorded as an AE, whereas the start of pregnancy will be recorded as the start date of the AE and the date of child birth will be recorded as the end date. Furthermore, the outcome of the pregnancy should be documented.

#### 9 Statistical Considerations

An independent qualified statistician will perform all statistical analyses.

The primary analysis will be conducted after all patients completed the 12-month follow-up visit. Optional interim analysis will be performed, as described in the SAP, after completion of the 8 weeks follow-up visit.

#### 9.2 Effectiveness analysis

A detailed description of the effectiveness analysis can be found in the statistical analysis plan (SAP).

#### Primary effectiveness analysis

The primary efficacy objective of this study is to confirm safety and performance of SLActive® implants by means of bone level change 12 months after implant loading.

To assess if SLActive® implants have a change in bone level compared to SLA® a repeated measures model may be used. Given the effects of treatment, quadrant, site, subjects, description of implant, time between measurements and possibly other variables (that could

have an effect on the change in bone level over time), a repeated measures analysis should be used to determine if there is any treatment effect.

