# 3.4.2 Secondary Endpoints

The secondary objectives assessed are:

- Bone level change (between implant placement and loading and between loading and 12 months after implant loading)
- Changes of biomarkers in GCF in regards to:
  - Inflammation (between implant placement and 30 days):
     Anti-inflammatory biomarkers analysis (concentrations of IL-10 and IL-4)
     Inflammatory biomarkers (concentrations of IL-6, IL-1β, TNF-α, IL-2)
  - Osseointegration (between day 7 and 8 weeks):
     Concentrations of VEGF, Osteocalcin (OCN), Osteopontin (OPN)
- Bacterial load analysis (between implant placement and 30 days)
- Implant stability (with ISQ) (between implant placement and 8 weeks)
- Soft tissue/ wound healing (Landry index) (between suture removal and 14 days)
- Clinical measurements
  - o Keratinized tissue height at implant placement and after 12 months
  - Probing pocket depths (PPD) and Bleeding on Probing (BoP) after 12 months. It is not the idea to evaluate a change but rather the occurrence after 12 month and possible differences between groups as these parameters are an indicator to determine the incidence of peri-implant diseases.
  - o FMPS (at screening and after 12 months)
- Implant survival
- Prosthetic success (prosthetic survival and mechanical complications acc. to ITI Treatment Guide Volume 8 (37))

Patient satisfaction (OHRQoL, OHIP-14 questionnaire) (at screening, loading and after 12 months)

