# **6.3** Implant placement, sampling (baseline) (Visit 2, day 0)

The eligibility criteria need to be re-evaluated prior to implant placement to confirm eligibility. Straumann® BLT, Roxolid®, SLActive® and SLA® implants need to be placed in the assigned study quadrants as described in Section 3.3 (study treatment) and Section 0 (randomization) and recommendations given by the manufacturer. Blinding is applicable as described in section 0. **Note**: if there is no control and test implant available (one of each) that qualify as study implants (implant is assessed as primary stable (as defined in Section 7.2.3) at surgery, the abutment torque is at least 15 Ncm at surgery and the implant site fulfills the eligibility criteria, see Section 3.3 for further details), in 2 different quadrants, the patient needs to be **withdrawn** (see section 3.7.3).

Surgical procedure, implant placement, final abutment insertion and postoperative patient instructions are performed and documented as described in section 7.2.3.

The following evaluations will be performed and documented at this Visit, which are described in detail in **Section 7** 

- Review of the patient eligibility (inclusion and exclusion criteria)
- Randomization (before implant placement but after the preparation of the bed where the first implant will be placed, see Section 0 for further details)
- Documentation of surgical procedure and implant placement (see Section 7.2.3.)
- Periapical X-ray
- ISQ
- KM (buccal)
- AEs and device deficiencies
- Changes in concomitant medications and procedures
- Photographs of the implant site

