## 9.4 Sample size

The primary hypothesis is that 12 months after loading, the marginal bone loss around the SLActive® implants will not be appreciably greater than around the SLA® implants.

In the case of MBL, where smaller values are better, the null and alternative hypotheses can be stated as follows:

 $H_0$ : Mean MBL for the test >= Mean MBL for the control + tolerance range  $H_A$ : Mean MBL for the test < Mean MBL for the control + tolerance range

The tolerance range or non-inferiority margin characterizes the largest absolute difference which is considered to be dismissible. A MBL of less than 0.5mm within the first year after implant loading constitutes an acceptable clinical standard (28, 45, 46). In this clinical trial, a non-inferiority margin of 20% of the acceptable clinical standard was chosen, which amounts to 0.1mm.

Based on Karabuda et al (28) who compared MBL in SLActive® and SLA® implants one year after loading, if it is assumed that the mean and SD would be  $0.46 \text{mm} \pm 0.20 \text{mm}$  for SLA® and for the scenario of  $0.43 \text{mm} \pm 0.22 \text{mm}$  for the SLActive® (with a correlation=0.0), that a difference of 0.10 mm or less is unimportant and that the alpha (one tailed) is set to 0.05, then with a sample size of 51 patients (51 pairs, a pair within a patient), the study will have a power of 92.4% to show that the mean MBL for the SLActive® surface is at least as low as the mean for the SLA®. The null hypothesis is then, that the mean for the SLActive® is 0.10 mm higher than the mean for the SLA®, and that the study has a power of 92.4% to reject this null hypothesis.

The Proc Power procedure of the software SAS v9.4, SAS Institute AG, Cary NC USA was used for calculations

60 patients will be enrolled in order to take into account a 20% dropout rate.

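### Section 9.2 does not name each implant's own Visit 2 value among the model effects for bone level, ISQ and keratinized tissue; its use should be pre-specified

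*Combined protocol and SAP*

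**What the plan says.** Section 9.2 (primary effectiveness analysis) proposes, in permissive wording, a repeated measures model for bone level change, "Given the effects of treatment, quadrant, site, subjects, description of implant, time between measurements and possibly other variables". The list is open-ended and does not name the implant's value at placement. For quantitative secondary endpoints the section also plans repeated measures modelling, controlling for whatever is expected to matter, and names no covariate. It refers to a SAP for the detail; that text is not part of the document reviewed.

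The starting values are collected:
- **Bone level:** section 6.3 lists a "Periapical X-ray" at Visit 2. Section 7.3.1.2 measures bone level from the implant shoulder to the first bone contact seen on the film, averages mesial and distal, and forms change by subtracting one visit from another.
- **ISQ:** section 3.4.2 lists "Implant stability (with ISQ) (between implant placement and 8 weeks", and Table 2 schedules it at Visits 2 and 6.
- **Keratinized tissue:** Table 2 schedules it at Visits 2 and 9.

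Section 9.4 plans the primary comparison as a paired test with no covariate.

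**The concern.** In a split-mouth trial the subject effect removes differences between patients. Quadrant identifies the jaw, and centre and implant description are also listed. None of these removes the remaining difference between the two implants of a pair in how each started: bone level on the placement film, stability achieved at insertion, and height of keratinized tissue at that site. The Visit 2 value measures this directly.

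Two things are at stake. The first is precision. The primary margin is "which amounts to 0.1mm" against a planned SD of pair differences of about 0.30 mm, and a plain change score for ISQ carries the full noise of the first reading. The second is analyst freedom. With an open covariate list, whether the starting value enters can be decided after the data are seen, and a non-inferiority conclusion could turn on that choice.

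**Working it through.** **Inputs from section 9.4.** SD 0.20 mm (SLA) and 0.22 mm (SLActive), correlation 0, means 0.46 and 0.43 mm (true difference −0.03 mm), margin 0.10 mm, and "the alpha (one tailed) is set to 0.05". The plan states that with "51 patients (51 pairs, a pair within a patient), the study will have a power of 92.4"%.

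**Reproducing the plan's figure.**
- SD of the pair difference = √(0.20² + 0.22²) = 0.2973 mm.
- Standard error = 0.2973/√51 = 0.0416 mm.
- Non-centrality = (0.10 + 0.03)/0.0416 = 3.12.
- Non-central t with 50 df, one-sided 5%: power 92.4%. This agrees with the plan.
- If the surfaces are truly equal: non-centrality 0.10/0.0416 = 2.40, power 76.6%.

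**Adding the Visit 2 value.** Let r be the correlation between the within-pair Visit 2 difference and the within-pair outcome difference. The documents do not give r; the range below is an assumption. Residual SD = 0.2973 × √(1 − r²), with one df removed (49 df).

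| r | Residual SD (mm) | Power, true difference −0.03 mm | Power, surfaces equal | Interval narrower by |
|---|---|---|---|---|
| unadjusted | 0.297 | 92.4% | 76.6% | – |
| 0 | 0.297 | 92.4% | 76.5% | 0% |
| 0.1 | 0.296 | 92.6% | 76.9% | 0.5% |
| 0.2 | 0.291 | 93.3% | 78.0% | 2.0% |
| 0.3 | 0.284 | 94.3% | 79.9% | 4.6% |
| 0.5 | 0.257 | 97.2% | 86.2% | 13.4% |

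**Worst case.** The table charges only the lost df. Chance imbalance in the covariate also inflates the variance, on average by 1 + 1/(51 − 3) = 49/48. At r = 0 the non-centrality becomes 3.12/√(49/48) = 3.09 and power 92.0%, under half a point below the plan (75.8% if the surfaces are equal). Gain and cost balance where (1 − r²) × 49/48 = 1, that is r = 1/7, about 0.14.

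**ISQ and keratinized tissue.** Let rho be the correlation between the first and last within-pair differences, with equal variances σ². A change score has variance 2σ²(1 − rho); the adjusted analysis has σ²(1 − rho²). The ratio is (1 + rho)/2: 0.65, 0.75, 0.85 and 0.95 at rho = 0.3, 0.5, 0.7 and 0.9. A simulation with 51 pairs gave 0.65, 0.77 and 0.87 at 0.3, 0.5 and 0.7.

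**The case against.** A reader might infer that the plan makes no baseline adjustment at all. The documents do not support that. The effect list is open, the detail is deferred to the SAP, and a repeated measures model that keeps Visit 2 as an outcome row with a common mean would recover nearly all of the gain. They do not say whether this is intended, so what stands is that the handling is unspecified.

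A reader might also infer a definite loss of power on the primary endpoint. That is not shown. Section 7.2.3 standardises the shoulder at 1 mm subcrestal. With bone level measured from the shoulder to first bone contact, many placement readings may lie near zero with little spread. Below r of about 0.2 the gain is under one point. The regression-to-the-mean argument applies to bone level only if the primary change starts at placement, and section 3.4.1 does not name the starting visit. This objection stands for bone level; it has less force for ISQ and keratinized tissue, whose starting values are not standardised in this way.

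Nor are ISQ and keratinized tissue ranked above other secondary endpoints. The secondary hypotheses concern biomarkers, and the osseointegration markers have no placement sample. A signed shoulder-to-crest depth would be a different reading from the one section 7.3.1.2 defines, so it cannot be assumed available.

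Finally, randomization precedes placement (section 7.2.1), so the Visit 2 film and ISQ follow allocation. Section 7.2.2 separates assessor from operator and masks the patient, but does not say that the operator is blinded. Adjustment therefore assumes that the surface, and knowledge of it, did not affect the Visit 2 value. That is plausible for a surface effect within one visit, but it should be stated and checked.

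**Conclusion.** The point holds as an unspecified and nearly free improvement. Section 9.2 leaves each implant's Visit 2 value off its named effects although all three measures are collected, and the other listed effects do not replace it.

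The planned 92.4% power reproduces without adjustment and does not depend on it. Under the plan's inputs, adjustment moves power from 92.4% at r = 0 to 97.2% at r = 0.5, or from 76.6% unadjusted to 79.9% (r = 0.3) and 86.2% (r = 0.5) if the surfaces are equal. All of these gains rest on an r that the documents do not supply, and for bone level it may be low. The clearer case is ISQ and keratinized tissue, if the alternative is a plain change score. The downside is bounded at about one df, under half a point of power at the planned difference.

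**What to change.** State in section 9.2 and in the SAP:

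1. Week-8 ISQ and 12-month keratinized tissue are analysed with the implant's Visit 2 value as a fixed covariate, or with Visit 2 as an outcome row whose mean is common to both surfaces. Subject stays as the pairing factor.
2. The Visit 2 bone level, as section 7.3.1.2 defines it, enters the primary bone-level model in the same way. Name the starting visit of the primary change at the same time.
3. No model adjusts for values taken from week 1 to loading, which the surface may already have changed.
4. Using the Visit 2 film and ISQ assumes no immediate effect of the surface. The unadjusted result is reported as a sensitivity analysis.

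The cost is wording only. No new visit, film or reading is needed, because the covariates are values already scheduled. Each model loses about one degree of freedom. The sample size need not change.

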# 2 Objectives

#### 2.1 Study Hypothesis

Based on previous obtained data the expectations are as follows:

Co-primary study hypotheses:

- 1) SLActive® implants are safe
- 2) 12 months after loading, the marginal bone loss around the SLActive® implants will not be appreciably greater than around the SLA® implants.

Secondary study hypotheses:

- SLActive® implants show superior osseointegration compared to SLA® as tested by biomarker analysis
- 4) SLActive® implants show superior anti-inflammation compared to SLA® as tested by biomarker analysis

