# 3.4 Endpoints

#### 3.4.1 Primary Endpoint

The following parameter will be measured as primary endpoint:

- Bone level change 12 months after implant loading.
- Occurrence of adverse device effects and device deficiencies that could have led to a serious adverse device effect

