# Secondary effectiveness analysis

The secondary endpoints as listed in Section 3.4.2 will be compared between the treatment groups for the time points recorded (Table 2). Comparisons between the treatment groups will be based on 95% confidence intervals.

Beyond the secondary endpoints in the secondary hypotheses, all stated quantitative secondary endpoints should be analyzed using repeated measures modeling. This will control for any effects expected to be significant. The response and/or explanatory variables may need to be transformed depending on their ability to meet the assumptions of the model.

Through using repeated measures modeling and the randomization scheme proposed we may disregard any specific implant within quadrant randomization and the need to limit measure comparisons between two implants alone. This maintains result integrity by including all information in the analysis. Furthermore, secondary variables that have measures across more than two time-points are analyzed with these methods with no loss in data.

The survival analysis will be carried out over the study implants (study control and study test implant) placed at the surgery visit (V2) and within the ITT population. Implant survival will be analyzed using the Kaplan-Meier Survival estimate with Confidence Intervals (CI) given by the Greenwood formula. Considering that for this study the number of patients not completing the 12 months follow-up visit may exceed 5% due to missed follow-up visits, the formula of Rothman will used for confidence intervals.

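### Section 9.2 words the primary analysis as a search for any treatment effect and does not tie it to the one-sided 0.10 mm non-inferiority test that section 9.4 defines and powers

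*Combined protocol and SAP*

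**What the plan says.** Section 2.1 gives the co-primary performance hypothesis in words: 12 months after loading, "the marginal bone loss around the SLActive® implants will not be appreciably greater than around the SLA® implants".

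Section 9.4 turns this into a formal test. The null hypothesis is that mean loss with SLActive is at least the SLA mean plus a tolerance. The tolerance is fixed: "In this clinical trial, a non-inferiority margin of 20% of the acceptable clinical standard was chosen, which amounts to 0.1mm". The error rate is given by the assumption "that a difference of 0.10 mm or less is unimportant and that the alpha (one tailed) is set to 0.05". Power is stated as 92.4% with 51 pairs.

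Section 9.2, under the primary effectiveness analysis, describes the analysis itself. It begins "To assess if SLActive® implants have a change in bone level compared to SLA® a repeated measures model may be used", lists covariates, and ends by saying that "a repeated measures analysis should be used to determine if there is any treatment effect". That paragraph contains no margin, null hypothesis, alpha, sidedness, confidence limit or criterion for success, and no reference to 9.4. The opening line of 9.2 refers the reader to a SAP for detail. No separate SAP text was available for this review.

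**The concern.** The protocol sizes the trial for one question and words its primary analysis as another. Asking whether there is any treatment effect points to a comparison with zero. The primary hypothesis needs a comparison with 0.10 mm, in one direction.

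The two comparisons can give different answers. Not rejecting zero does not show that the difference is below the margin, and a model result reported only as effect present or absent leaves the non-inferiority question unanswered. The risk is greatest if a non-significant difference were taken to confirm performance, because the error rate for a surface worse by the margin would then no longer be the 5% that section 9.4 sets.

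**Working it through.** **Inputs (section 9.4).** SD 0.20 mm (SLA) and 0.22 mm (SLActive); means 0.46 and 0.43 mm, so the true difference SLActive minus SLA is −0.03 mm; correlation 0; 51 pairs; margin 0.10 mm; one-sided alpha 0.05.

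**Step 1: reproduce the plan's power.** Paired t-test with the noncentral t distribution, 50 degrees of freedom.

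- SD of the difference = √(0.20² + 0.22² − 2·r·0.20·0.22). At r = 0 this is √0.0884 = 0.2973 mm.
- Standard error = 0.2973/√51 = 0.0416 mm.
- Noncentrality = (0.10 + 0.03)/0.0416 = 3.12; critical value t(0.95; 50) = 1.676.
- Power = 92.4%, which matches section 9.4. The sample size statement is correct on its own inputs.

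**Step 2: what the 9.2 wording could yield.** Section 9.2 gives no level or null, so two assumptions are needed:

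- (a) the analysis is a two-sided 5% test of zero difference, critical value t(0.975; 50) = 2.009;
- (b) a non-significant result is read as no appreciable difference.

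Take a true difference equal to the margin, +0.10 mm. The 9.4 test would wrongly declare non-inferiority in 5% of trials. Under (a), the probability of a non-significant result is the noncentral t probability between −2.009 and 2.009, with noncentrality 0.10/SE. Section 9.4 assumes correlation 0; 0.3 and 0.5 are assumed here to give a range.

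| Correlation | SD of difference (mm) | SE, 51 pairs (mm) | Noncentrality | P(non-significant), true +0.10 mm | Error allowed by 9.4 |
|---|---|---|---|---|---|
| 0 | 0.2973 | 0.0416 | 2.40 | 34.6% | 5% |
| 0.3 | 0.2490 | 0.0349 | 2.87 | 19.7% | 5% |
| 0.5 | 0.2107 | 0.0295 | 3.39 | 8.6% | 5% |

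**Step 3: one concrete result.** Suppose SLActive shows 0.06 mm more loss, with the SD of the difference as assumed at correlation 0.

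- Against zero: t = 0.06/0.0416 = 1.44, two-sided p = 0.16, so no treatment effect is found.
- Against the margin: upper limit of the two-sided 90% interval = 0.06 + 1.676 × 0.0416 = 0.130 mm, above 0.10 mm, so non-inferiority is not shown.

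The same data pass as no effect and fail the primary hypothesis.

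**The case against.** The best defence is that nothing essential is missing from the protocol as a whole. Section 9.4 labels the non-inferiority statement the primary hypothesis and gives its null, margin and alpha; section 2.1 agrees; section 9.2 withdraws none of this. A repeated measures model can supply the estimate and interval that the test needs, and a SAP is the usual place for the exact rule. All of that stands. It limits the point to a mismatch of wording and linkage within the protocol. It does not remove it, because 9.2 states an aim for the primary analysis, and that aim is not the one in 9.4.

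Some stronger readings go beyond the text:

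- *A reader might infer that the trial has no non-inferiority rule, or has switched to a test of difference.* The documents do not support this: 9.4 contains the test, and 9.2 specifies no null or alpha to replace it.
- *A reader might infer that the trial is badly underpowered*, since a two-sided 5% test of zero has only 10.9% power at −0.03 mm with 51 pairs. That is the power of a test the protocol does not specify.
- *A reader might look for one rate at which 9.2 and 9.4 disagree.* At −0.03 mm and correlation 0 it is about 7% if non-significance counts as success, and about 82% if success means rejecting zero in favour of SLActive. The documents do not say which applies. Nor does the rate of trials that are non-significant yet fail the margin rise steadily as the surface gets worse: it is about 46% at a true +0.05 mm, 30% at +0.10 mm and 6% at +0.15 mm.
- *A reader might carry over the sentence* "Comparisons between the treatment groups will be based on 95% confidence intervals" *to the primary endpoint.* It stands under the secondary analysis and follows a sentence about secondary endpoints, so it does not govern the primary one.

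**Conclusion.** The point holds as a mismatch within the protocol that should be fixed. Sections 2.1 and 9.4 define and power a one-sided non-inferiority test; section 9.2 describes the primary analysis as a search for any effect and, as written, does not decide that hypothesis. The 92.4% power figure is right and is not in question.

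The error rates of about 35%, 20% and 9%, against 5%, illustrate what could go wrong. They rest on assumptions (a) and (b), the 9.4 SDs, 51 pairs and an unadjusted paired analysis, and they shrink as the within-patient correlation rises. The textual mismatch does not depend on them. Confidence is moderate, because the SAP may already state the rule; in that case only the protocol wording needs aligning.

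**What to change.** In section 9.2, replace the wording about any treatment effect with:

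> The repeated measures model will be used to estimate the SLActive-minus-SLA difference in mean marginal bone loss at 12 months after loading; non-inferiority is concluded if the upper limit of the two-sided 90% CI (one-sided 95%) is below 0.10 mm (section 9.4).

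Check that the SAP states the same rule. With this rule the 92.4% power at 51 pairs applies unchanged. The cost is one sentence in the protocol and a consistency check of the SAP, with no extra patients, visits or data.

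A separate item for the sponsor, not part of this point: section 3.4.1 gives the primary endpoint as "Bone level change 12 months after implant loading" without a start point, while section 3.4.2 lists the change from loading to 12 months as secondary. The start point of the primary change should be confirmed on its own.
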